9.0 BACKGROUND THERAPEUTIC INFORMATION

9.1 Metformin (Please refer to the package insert for more comprehensive information.)

9.1.1 Availability: Metformin is commercially available

9.1.2 Other Names: Glucophage; Glumetza; 1,1-Dimethylbiguanide; Metiguanide; Diabex; Dimethylbiguanide; Metforminum; Diabetosan; Fluamine: a commercially available agent.

9.1.3 Chemical Name: 3-(diaminomethylidene)-1,1-dimethylguanidine

9.1.4 Molecular Formula: C₄H₁₁N₅

Metformin HCl is a white crystalline powder soluble in water and 95% ethyl alcohol. It is practically insoluble in ether and in chloroform. Melting Point: 218-220° C

9.1.5 Mode of Action:

Metformin HCl is a biguanide derivative producing an antihyperglycemic effect which can only be observed in man or in the diabetic animal and only when there is insulin secretion. Metformin, at therapeutic doses, does not cause hypoglycemia when used alone in man or in the non-diabetic animal, except when using a near lethal dose. Metformin has no effects on the pancreatic beta cells. The mode of action of metformin is not fully understood. It has been postulated that metformin might potentiate the effect of insulin or reduce hepatic gluconeogenesis. Metformin absorption is relatively slow and may extend over about 6 hours. The drug is excreted in urine at high renal clearance rate of about 450 mL/min. The initial elimination of metformin is rapid with a half-life varying between 1.7 and 3 hours. The terminal elimination phase accounting for about 4 to 5 % of the absorbed dose is slow

with a half-life between 9 and 17 hours. Metformin is not metabolized. Its main sites of concentration are the intestinal mucosa and the salivary glands. The plasma concentration at steady-state ranges about 1 to 2 mcg/mL. Certain drugs may potentiate the effect of metformin HCl, particularly sulfonylurea type of drugs in the treatment of diabetes. The simultaneous administration of these two types of drugs could produce a hypoglycemic reaction, especially if they are given in patients already receiving other drugs which, themselves, can potentiate the effect of sulfonylureas. These drugs can be: long-acting sulfonamides, tuberculostatics, phenylbutazone, clofibrate, monoamine oxidase inhibitors, salicylates, probenecid and propranolol. In healthy volunteers, the pharmacokinetics of propranolol and ibuprofen were not affected by metformin when co-administered in single-dose interaction studies.

Metformin is negligibly bound to plasma proteins and is, therefore, less likely to interact with highly protein-bound drugs such as salicylates, sulfonamides, chloramphenicol, and probenecid, as compared to sulfonylureas, which are extensively bound to serum proteins.

Human Toxicity

In man, no adverse effect has been reported on liver or kidney function, the hematopoietic system or on the blood vessels. The reported incidence of lactic acidosis in patients receiving metformin hydrochloride is very low (approximately 0.03 cases / 1000 patient/years with approximately 0.015 fatal cases / 1000 patient/years). The consecutive administration of both phenformin and metformin to the same patient has allowed for the demonstration of a fundamental difference between these two biguanides in relation to lactacidemia. In some instances, patients developed hyperlactacidemia with phenformin when the same patients were presenting normal lactic acid levels while being treated with metformin. In other instances, hyperlactacidemia observed during a treatment with phenformin did regress when metformin was substituted for phenformin. Metformin may increase lactacidemia but to a degree that is clinically less significant than the elevation seen after phenformin.

Teratology

Teratological studies were carried out in albino rats divided in three groups: No abnormalities were found, even when high doses were administered. The number of animals was the same in each group. Death rate in the three groups of treated animals and controls was approximately the same. However, the number of living animals in each group treated was slightly lower than in the control group. Also, the frequency of litters exceeding 10 live animals was slightly higher in the control group. A loss of weight at the time of weaning has been observed when compared to the control group. Nevertheless, on a statistical basis, differences were shown to be non-significant. There is no difference between the groups of treated animals and the control group regarding the number of stillborn. The number of deaths after birth was slightly higher in metformin treated groups than in the control group, but the

comparison of average death rates is not significant ($p > 0.05$).

9.1.6 How Supplied: It will not be provided by the study (Commercial supply)

9.1.7 Storage: Store at room temperature (15° to 30°C) in well-closed containers

9.1.8 Dose Specifics: 1000 mg twice daily orally, continuously to the end of study (for details of dose escalation please see Section 5.4.3). The tablets should be taken at approximately the same time every day.

9.1.9 Route of Administration: Metformin is administered orally, with food

9.1.10 Side Effects: Please refer to protocol section heading “Clinical Experience with Metformin” for a summary of adverse effects.

9.1.11 Dose Adjustments

Please see section 5.5.1.

9.1.12 Concomitant Therapy

Permitted

Subjects may receive bisphosphonates, at the discretion of their treating physician, before during or after randomization and study treatment with metformin.

Not permitted

Sulfonylureas, thiazolidenediones or insulin for any reason unless these drugs become necessary to treat a new diagnosis of diabetes mellitus while on study therapy in which case the patient will discontinue study treatment. Subjects should avoid excessive alcohol intake (i.e. less than 3 alcoholic beverages on any given day). Androgen deprivation therapy is not permitted.

9.2 Bicalutamide (Please refer to the package insert for more comprehensive information.)

9.2.1 Availability: Bicalutamide is commercially available

9.2.2 Other Names: Casodex®, a commercially available agent.

9.2.3 Chemical Name: Propanamide, N-[4-cyano-3-(trifluoromethyl)phenyl]-3-[4-fluorophenyl)sulfonyl]-2-hydroxy-2-methyl-,(+/-)

9.2.4 Molecular Formula: C₁₈H₁₄N₂O₄F₄S

9.2.5 Mode of Action: Competitive inhibitor of androgen binding to cytosolic androgen receptors.

9.2.6 How Supplied: White, film-covered oral tablet containing 50 mg of bicalutamide. It will not be provided by the study (Commercial supply)

9.2.7 Storage: Controlled room temperature, 20-25°C.

9.2.8 Dose Specifics: 50 mg/daily orally beginning Cycle 3 (week 13), continuously to the end of study (please see Section XXX). The tablet should be taken at approximately the same time every day.

9.2.9 Route of Administration: Oral, may be taken with or without food.

9.2.10 Side Effects:

The most serious side effect that has been associated with bicalutamide is severe liver injury, which has been reported in approximately 1% of patients in controlled clinical trials. Hepatotoxicity typically occurs within the first three to four months of continuous treatment. It is not known whether the regimen used in this trial can cause liver injury. Transaminase levels will be drawn every 4 weeks. Other common side-effects of bicalutamide overlap those of leuprolide acetate, including hot flashes, generalized pain, asthenia, constipation, diarrhea, nocturia, testicular atrophy, and gynecomastia.

10.0 ADVERSE EVENTS

10.1 Definition of Adverse Experience

10.1.1 Adverse Events (AE) is any unfavorable and unintended sign (including an abnormal laboratory finding), symptom or disease temporally associated with the use of a medicinal (investigational) product, treatment or procedure regardless of whether it is considered related to the medical treatment or procedure (*NCI CTEP Guidelines March 28, 2011*).

10.1.2 Serious Adverse Event (SAE) is an AE that is fatal or life threatening, requires inpatient hospitalization or prolongation of existing hospitalization (for > 24 hours), persistent or significant incapacity or substantial disruption of the ability to conduct normal life functions, or is a congenital anomaly/ birth defect, or results in any important medical event that may not result in death, be life threatening, or require hospitalization may be considered an SAE when, based upon appropriate medical judgment, may jeopardize the subject and may require medical or surgical intervention to prevent any of the above outcomes. A “life-threatening” adverse event places the patient at immediate risk of death in the judgment of the investigator or sponsor.

10.1.3 Severity Rating

The investigator will evaluate the severity of each adverse event. NCI Common Terminology Criteria for Adverse Events (CTCAE v.4.0) or study specific toxicity

tables provided in the protocol define severity. If not included in CTCAE v.4.0, severity is expressed in numerical grade using the following definitions:

1. Grade 1: Mild-asymptomatic or mild symptoms; clinical or diagnostic observations only; intervention not indicated.
2. Grade 2: Moderate-minimal, local or noninvasive intervention indicated; limiting age appropriate instrumental ADL.
3. Grade 3: Severe-severe or medically significant but not immediately life-threatening; hospitalization or prolongation of hospitalization indicated; disabling; limiting self care ADL.
4. Grade 4: Life-threatening consequences; urgent intervention indicated.
5. Grade 5: Death related to AE

10.1.4 Attribution/Relationship to study drug

- Definite – clearly related
- Probable – likely related
- Possible – may be related
- Unlikely – doubtfully related
- Unrelated – clearly not related

10.1.5 Expectedness

An Expected Adverse Event is one where the specificity or severity is consistent with the current information available from the resources.

An Unexpected Adverse Event is one where the nature, severity, or frequency of the event is related to participation in the research is not consistent with either:

1. The known or foreseeable risk of adverse events associated with the procedures involved in the research that are described in (a) the protocol-related documents, such as the IRB-approved research protocol, any applicable investigator brochure, and the current IRB-approved informed consent document, and (b) other relevant sources of information, such as product labeling and package inserts: or
2. The expected natural progression of any underlying disease, disorder, or condition of the subject (s) experiencing the adverse event and the subjects(s) predisposing risk factor profile for the adverse event.

(OHRP Guidance on reviewing unanticipated problems 2007)

10.2 Recording and Reporting Responsibilities

10.2.1 Investigative site recording responsibilities:

1. Upon identification of an AE or SAE, the site investigator will utilize the above definitions to properly classify the event. Each category listed above must be recorded for each event.
2. All AEs and SAEs will be recorded in the “AE case report forms” (CRF)

and in progress reports with details about the grade and attribution of each episode, action taken with respect to the study drug, and the patient's outcome will be recorded in the CRF. All events will be recorded on case report forms for the duration of the study until they resolve.

3. All reportable SAEs will be recorded on the FDA MedWatch form 3500a. After submitting the initial report it may be necessary to submit follow up reports to the Sponsor should the event require further investigation.

10.2.2 Investigative site reporting responsibilities:

1. The investigator/ site is responsible to report all SAEs which occur on or after the first day of treatment to the sponsor within 24 hours of becoming aware of the event. All subsequent SAEs must be reported for up to 30 days after the last treatment.

2. Each investigator is responsible to report all AEs/SAEs to their local IRB following guidelines set by that IRB. The FCCC OCR reserves the right to request an event be reported to the IRB at their discretion. Copies of events reviewed by the IRB must be sent by email to [contact].

3. If the investigator or IRB feels the event warrants a revision to the informed consent that was not already initiated by the OCR, draft revisions will be made in track changes and submitted to the OCR for consideration. Any consent revisions must receive OCR approval **prior** to submission to the IRB.

4. Any investigator who is in doubt of whether a particular AE needs to be reported is directed to call the Study Monitor for confirmation with the Sponsor-Investigator.

5. If the results of an investigator or OCR investigation show an adverse event not initially determined to be reportable is so reportable, the investigator will report the event following the above guidelines based on the date the determination is made.

6. Copies of all related correspondence and reporting documents must be submitted to the ISRU and will be maintained in the trial master file.

The participating site should report events to:

Investigator-Sponsored Research Unit
Office of Clinical Research
Fox Chase Cancer Center
[contact]

10.2.3 Sponsor Reporting Responsibilities:

1. Adverse events which meet all of the following criteria must be reported to all participating institutions for IRB submission within 2 weeks of notification of the event.

i. Unexpected (in terms of nature, severity, or frequency) given (a) the research procedures that are described in the protocol-related documents,

such as the IRB-approved research protocol and informed consent document; and (b) the characteristics of the subject population being studied;

- ii. Possibly related to participation in the research (possibly related means there is a reasonable possibility that the incident, experience, or outcome may have been caused by the procedures involved in the research); and
 - iii. Serious (refer to above definition) or otherwise one that suggests that the research places subjects or others at a greater risk of physical or psychological harm than was previously known or recognized.
2. If the adverse event requires modification of the study protocol and informed consent, these changes will be provided to all participating institutions in the form of an amendment from the OCR for each site's IRB of record along with the report of the adverse event.
 3. Copies of all related correspondence and reporting documents will be maintained in a centralized regulatory file for this study at OCR.
 4. SAEs that are related, unexpected, fatal, or life-threatening are reportable through the Food and Drug Administration (FDA) MedWatch program by telephone or fax no later than 7 calendar days after initial receipt of the information. Further information on the timing of submissions are as directed by FDA guidelines (<http://www.fda.gov/medwatch/index.html>). Serious, unexpected events that suggest significant clinical risk will be submitted to within 15 calendar days after initial receipt of this information.

Food and Drug Administration:
 Telephone [name]
 Fax [name]
<http://www.fda.gov/medwatch/report.htm>

Mandatory Drug Reporting:
 Central Document Room
 Center for Drug Evaluation and Research
 Food and Drug Administration
 [name]
 [name]
 Office of Post-Marketing Drug Risk Assessment (HFD 730)
 Center for Drug Evaluation and Research
 Food and Drug Administration
 [name]
 [name]
 [contact] for any further questions regarding where to send drug mandatory reporting forms

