2.0 OBJECTIVES

2.1 Primary endpoint:

The proportion of patients with undetectable PSA (< 0.2 ng/mL) at 32 weeks with metformin plus bicalutamide compared to bicalutamide monotherapy.

2.2 Secondary endpoints:

- The proportion of patients with PSA decline > 85% at 32 weeks with metformin plus bicalutamide compared to bicalutamide monotherapy.
- The time to PSA progression with metformin plus bicalutamide compared to bicalutamide monotherapy.
- To evaluate the time to onset of radiographic evidence of metastatic disease (rPFS) with metformin plus bicalutamide compared to bicalutamide monotherapy.
- To characterize the PSADT changes pre-study, during treatment, and off treatment.
- To evaluate the safety and tolerability of metformin in this patient population.
- To evaluate QOL with metformin plus bicalutamide compared to bicalutamide monotherapy.
- To evaluate the time to next therapy (i.e. antiandrogen or GnRH antagonist/agonist).

2.3 Exploratory endpoints:

- Immunogenicity of bicalutamide +/- metformin by flow cytometric analysis of T-cell frequency, activation status, cytokine profiles, antibody levels and analysis of sCD27 and sCD40L
- Evaluate circulating PSA levels and correlations with immunogenicity and/ or efficacy

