5.3.1 Treatment ARM A

Cycles 1 – 2: Observation without treatment

Cycles 3 – 8: Bicalutamide 50 mg daily, orally, continuously to the end of study (week 32).

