5.3.2 Treatment ARM B

Cycles 1 - 2: In order to minimize gastrointestinal discomfort, metformin dosing will be ramped up over a period of 2 weeks. Metformin treatment will

be started at 500 mg BID (Dose Level -2) and increased by an increment of 500 mg daily every week +/- 2 days provided no grade 2 or higher gastrointestinal toxicity is noted. If grade 2 or greater gastrointestinal toxicity occurs during the first 4 weeks of treatment, the subject will be evaluated every 2 weeks until resolution of toxicity to grade 0 or 1 and, then, the metformin dose will be increased to the next dose level. The target dose of metformin is 1000 mg BID. If patient cannot tolerate higher dose, metformin will continued at maximum tolerated dose as listed below.

Dose level	Metformin dose
Dose Level -2 (Week 1 +/- 2 days)	500 mg twice daily
Dose Level -1 (Week 2 +/- 2 days)	500 mg breakfast / 1000 mg at bedtime
Dose Level 0 (Week 3 and later)	1000 mg twice daily

Cycles 3 – 8: Continue metformin at maximum tolerated dose (up to 1000 mg BID). Start bicalutamide 50 mg/daily, orally, on a continuous basis to the end of study (week 32).

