11.5 Safety Analyses

Safety analyses will be conducted on treated patients. All adverse events will be summarized 1) without regard to causal relationship and 2) by causal relationship to study drugs, based on the Investigator's opinion. Worst toxicity grades per subject will be tabulated for selected adverse events and laboratory measurements. Any serious adverse event or

adverse event resulting in premature and permanent discontinuation of any study drug will be described in detail. Adverse events and other symptoms will be graded according to the National Cancer Institute (NCI) Common Terminology Criteria for Adverse Events (CTCAE) Version 4.0

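### The start of 24-hour SAE reporting is undefined for arm A; read literally, that arm's weeks 1–8 fall outside sponsor reporting, and Section 11.5 plans no tabulation of that period by randomised arm

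*Combined protocol and SAP*

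**What the plan says.** Section 10.2.2 obliges each site to "report all SAEs which occur on or after the first day of treatment to the sponsor within 24 hours". The window closes as follows: "All subsequent SAEs must be reported for up to 30 days after the last treatment".

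The arms do not start drug together. For arm A, Section 5.3.1 reads "Cycles 1 – 2: Observation without treatment", with bicalutamide from Cycle 3 to week 32. For arm B, the dose table in Section 5.3.2 places the first metformin level in week 1.

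On recording, as distinct from reporting, Section 10.2.1 requires every AE and SAE to go on the case report forms (CRFs) for as long as the study lasts, without limiting this by arm or by first dose. Table 1 schedules AE recording from the Cycle 2 visit onward for all patients. Section 6.3 adds a toxicity assessment on Day 1 of each cycle.

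On analysis, Section 11.5 says "Safety analyses will be conducted on treated patients". Section 11.4 defines treated subjects by receipt of bicalutamide (arm A) or of bicalutamide and metformin (arm B). One secondary endpoint in Section 2.2 is "To evaluate the safety and tolerability of metformin in this patient population".

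**The concern.** The reporting clock is tied to an event that one arm reaches eight weeks later than the other, or to an event that the text leaves undefined for that arm. Sites could apply the rule differently. On the literal reading, an arm B patient hospitalised in week 4 triggers a 24-hour report, and an arm A patient hospitalised in the same week does not. Section 12.1 describes real-time SAE review by the ISRU and the Sponsor-Investigator. If that review draws on the expedited reports, it would receive more of arm B's events than arm A's for reasons unrelated to metformin.

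Weeks 1–8 also hold the only comparison of metformin with no drug, which bears directly on the metformin safety objective. Section 11.5 plans no tabulation by period. The bicalutamide-based definition in Section 11.4 would also leave out patients in either arm who stop before Cycle 3, including any arm B patient who leaves because of early metformin toxicity.

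**Working it through.** **Inputs.** Cycle length is 28 days (Section 5.3). Duration is 8 cycles, 32 weeks (Section 5.6). Arm A starts bicalutamide in Cycle 3 (5.3.1), and arm B starts metformin in week 1 (5.3.2). Reporting ends 30 days after last treatment (10.2.2). Planned totals are 22 in arm A and 44 in arm B (11.1).

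**The plan's own figure.** 8 × 28 = 224 days = 32 weeks, which agrees with Section 5.6.

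**Start of Cycle 3.** 2 × 28 + 1 = day 57, the first day of week 9. Section 9.2.8 instead labels Cycle 3 as week 13, which on 28-day cycles is the start of Cycle 4. These passages must be reconciled.

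**Literal reporting windows, patients completing treatment.** Window = last treatment day + 30 − first treatment day + 1.

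- Arm B: 224 + 30 − 1 + 1 = 254 days.
- Arm A: 224 + 30 − 57 + 1 = 198 days.
- Difference: 254 − 198 = 56 days, all in weeks 1–8. Ratio: 254 / 198 = 1.28.
- With the week 13 label: 224 − 84 + 30 = 170 days for arm A, ratio 254 / 170 = 1.49.

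**Illustration for sponsor-reported SAEs only.** The documents give no SAE rate. Assume a constant rate that is equal in both arms, so there is no drug effect. The share with at least one reported SAE is 1 − exp(−rate × days / 365.25). The last column is 22 × [1 − exp(−rate × 56 / 365.25)].

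| Assumed rate per person-year | Arm A, 198 days | Arm B, 254 days | Arm A patients of 22 with an SAE in weeks 1–8 |
|---|---|---|---|
| 0.1 | 5.3% | 6.7% | 0.3 |
| 0.2 | 10.3% | 13.0% | 0.7 |
| 0.4 | 19.5% | 24.3% | 1.3 |

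**CRF capture in the same weeks.** Evaluations fall on Day 1 of each cycle, so the Cycle 2 visit looks back over weeks 1–4 and the Cycle 3 visit over weeks 5–8, in both arms. At full accrual and without dropout this is 22 × 8 = 176 arm A and 44 × 8 = 352 arm B patient-weeks. Section 13.1 asks for CRFs within 2 weeks of a visit. An arm A event just after Cycle 1 Day 1 that is picked up only at the next visit could therefore reach the sponsor about 28 + 14 = 42 days later. On the literal reading, the consequence for such an event is delay; it is not lost from the trial data.

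**The case against.** The strongest reply is that week 9 is not arm A's first treatment day at all. Section 4.1 requires participants to begin protocol treatment within 7 days of registration and records those who receive none as withdrawn. If treatment meant drug only, no arm A patient could comply. Section 5.6 counts treatment as 8 cycles without distinguishing arms, Table 1 labels all eight as treatment cycles, and the observation period is listed under the arm A treatment heading. This reading is reasonable. It does not settle the matter, because Section 5.3.1 expressly calls those cycles untreated and Section 11.4 identifies arm A's treated subjects by bicalutamide. The trigger is ambiguous. Section 10.2.2 does direct an investigator in doubt to call the Study Monitor, but that does not define the start date.

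The second reply is that a notification clock does not determine the safety dataset. This stands. A reader might infer that arm A has no safety data in weeks 1–8, that the planned safety tables will show an inflated SAE proportion in arm B, or that the Data Safety Monitoring Board (DSMB) will see a distorted comparison. The documents support none of these. CRF recording covers both arms, Section 11.5 summarises all adverse events and not only expedited ones, and nothing in Sections 12.2 or 13.1 confines the DSMB to expedited reports.

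It is also fair to say that splitting the tables by period improves the plan and does not correct an arithmetical error.

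**Conclusion.** The point holds in a limited form. The reporting trigger in Section 10.2.2 is undefined for arm A. On the literal reading, arm A's SAEs in weeks 1–8 fall outside 24-hour sponsor reporting, with windows of 198 versus 254 days. Those figures assume 28-day cycles, bicalutamide starting on day 57 and completion of all eight cycles. On the Cycle 1 Day 1 reading the gap disappears and only unclear wording remains.

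The percentages illustrate sponsor-reported SAEs at assumed rates and do not describe any table in the plan. At those rates, roughly 0.3 to 1.3 arm A patients would have an SAE in the affected weeks. No error rate or sample size changes, and the toxicity rule in Section 11.2 uses arm B only.

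Separately, the CRFs will hold the metformin-versus-observation data, but Sections 11.4 and 11.5 do not plan to tabulate that period. As worded, they would restrict it to patients who went on to bicalutamide.

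**What to change.** - **Section 10.2.2:** start SAE reporting to the sponsor at Cycle 1 Day 1 (or at randomisation) in both arms, and align the use of the word treatment with Sections 4.1, 5.3.1 and 5.6. From Cycle 1 Day 1, each arm then has 224 + 30 = 254 days for patients who complete treatment.
- **Section 11.5:** from the CRF data already collected, tabulate adverse events for weeks 1–8 and weeks 9–32 separately by randomised arm. Include arm A's observation period and patients in either arm who leave before starting bicalutamide, with a matching change or exception to the definition in Section 11.4.
- **Section 9.2.8:** reconcile the week 13 label with the cycle definition.

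The cost is a few sentences, a small number of extra arm A expedited reports and one additional table split. No new visits are needed, since arm A already attends at these times.
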